6.2.3 Visit 1 (V1) (6-9 months)

The following data may be collected and documented on the source (paper or subject's an electronic medical record):

- Documentation of relevant patient history and symptoms – SOC
- Medical History (including comorbid conditions) – SOC
- Vital signs (temperature, heart rate, blood pressure, respiratory rate, and pulse oximetry) including weight and height - SOC
 - Including optional noninvasive, optical hemoglobin measurement
- Concomitant Medications – SOC
- PFT's - SOC
- 6MWTs – SOC
- Completion of MRI screening form - research
- MRI Imaging session – research
 - Cardiac MRI
 - ^{129}Xe MRI
- Serum Pregnancy testing for a female of childbearing potential - research
 - Urine pregnancy test (if applicable) performed outside the 48hrs window
- Adverse event reporting – research
- Standard dose CT - research

CONFIDENTIAL

This document is confidential and the property of the Duke University.

7 Statistical Plan

7.1 *Sample Size Determination*

Power calculation: Based on the ^{129}Xe MRI metrics from our study (Wang, et al., 2019), we expect that we could detect an absolute difference of high barrier uptake of 10% between the post-COVID subjects and an existing cohort of healthy controls. We assume that with a standard deviation of 10% high barrier uptake within patients, and requiring a power of 90%, that a two-sided test would require a sample size of 23 to detect a difference. However, given that high-barrier uptake is expected only in the post-COVID group, a one-sided test suggests the proposed sample size has 99% power to detect a significant difference.

7.2 *Statistical Methods*

^{129}Xe MRI metrics will include RBC/barrier, barrier/gas, RBC/gas, and several spectroscopic indices. Continuous data will be presented using the mean \pm SD if normally distributed and median with 25th and 75th percentiles otherwise. We are fortunate to be able to compare the findings in our images to a database of approximately 30 healthy reference subjects whom we have scanned to date. These subjects have undergone the same ^{129}Xe MRI protocol and were recruited with no histories of smoking or cardiopulmonary disease, FEV1>80%, FEV1/FVC>0.70 and DLCO >80%. For subjects to be included in the reference cohort they further had a ventilation defect percentage \leq 6%, (upper limit of normal VDP (Ebner '19)) as well as RBC/barrier \geq 0.45 (at TR=15 ms), and image SNR>5, based on the Rose criterion. Comparisons between these groups will use analysis of variance (ANOVA) methods or Kruskal-Wallis test as appropriate.

8 Safety and Adverse Events

8.1 *Overview*

As the sponsor of the study, Duke University Medical Center and the Principal Investigator shall be solely responsible for complying, within the required timelines, any safety reporting obligation to competent Health Authorities, IRB and any participating (co or sub) investigators, as defined in applicable laws and regulations. For this protocol, safety data include adverse events and special situations, including pregnancies.

8.2 *Management of Safety data*

This study has been designated as an interventional study. As such, all adverse events, special situations including pregnancies and product quality complaints will be reported as described in this protocol from the time a subject has signed and dated an Informed Consent Form (ICF) until 30 days after the last documented use of the study drugs (i.e., end of study (9 months)).

Adverse Event

An **adverse event** (AE) is any symptom, sign, illness, or experience that develops or worsens in severity during the study. Intercurrent diseases or injuries should be regarded as adverse events. Abnormal results of diagnostic procedures are considered to be adverse events if the abnormality:

CONFIDENTIAL

This document is confidential and the property of the Duke University.

- results in study withdrawal
- is associated with a serious adverse event
- is associated with clinical signs or symptoms
- is associated with Abnormal lab values
- leads to additional treatment or to further diagnostic tests
- is considered by the investigator to be of clinical significance

Serious Adverse Event

Adverse events are classified as serious or non-serious. A ***serious adverse event*** is any AE, that is:

- fatal
- life-threatening
- requires or prolongs hospital stay
- results in persistent or significant disability or incapacity
- a congenital anomaly or birth defect
- an important medical event

Important medical events may not be immediately life-threatening but are clearly of major clinical significance. They may jeopardize the subject and may require intervention to prevent one of the other serious outcomes noted above. For example, drug overdose or abuse, a seizure that did not result in an in-patient hospitalization, or intensive treatment of bronchospasm in an emergency department would typically be considered serious.

All adverse events that do not meet any of the criteria for serious should be regarded as ***non serious adverse events***.

NOTE: DEATH FOR ANY REASON WILL BE REPORTED AS A SERIOUS ADVERSE EVENT.

Post-study Adverse Event

The investigator should follow all unresolved adverse events until the events are resolved, the subject is lost to follow-up, or the adverse event is otherwise explained. At the last scheduled visit, the investigator should instruct each subject to report any subsequent event(s) that the resident, or the subject's physician, believes might reasonably be related to participation in this study. The investigator should notify the study sponsor of any death or adverse event occurring at any time after a subject has discontinued or terminated study participation that may reasonably be related to this study. The sponsor should also be notified if the investigator should become aware of cancer development or a congenital anomaly in a subsequently conceived offspring of a subject that has participated in this study.

Hospitalization, Prolonged Hospitalization or Surgery

Any adverse event that results in hospitalization or prolonged hospitalization should be documented and reported as a serious adverse event unless specifically instructed otherwise in

CONFIDENTIAL

This document is confidential and the property of the Duke University.

this protocol. Any condition responsible for surgery should be documented as an adverse event if the condition meets the adverse event criteria.

Neither the condition, hospitalization, prolonged hospitalization, nor surgery is reported as an adverse event in the following circumstances:

- Hospitalization or prolonged hospitalization for diagnostic or elective surgical procedures for a preexisting condition. Surgery should *not* be reported as an outcome of an adverse event if the surgery's purpose was elective or diagnostic, and the outcome was uneventful.
- Hospitalization or prolonged hospitalization for therapy of the study's target disease, unless it is a worsening or increase in hospital admissions frequency as judged by the clinical investigator.

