Although the initial presentation of patients with moderate to severe symptoms of COVID19 infections is dominated by respiratory symptoms, 10% go on to develop persistent post-infection symptoms which are thought to have an inflammatory etiology. Evidence suggests that pathologic activation of the inflammasome persists beyond the acute initial presentation that contributes to the persistent disabling symptoms characterized as “long-haul COVID”. For this trial, subjects will be eligible for enrollment if they are outpatients with a history of a laboratory confirmed diagnosis of COVID-19 infection, and after 60 days or longer. We will enroll 13 subjects who continue to have respiratory symptoms (i.e., cough, shortness of breath, dyspnea on exertion). An additional 10 subjects engaged in competitive sports and diagnosed with COVID-19 will also be enrolled. These subjects can be asymptomatic or mildly to moderately. Although rare, cardiac impairment has been documented in <2% of these

CONFIDENTIAL

This document is confidential and the property of the Duke University.

individuals. To our knowledge, XeMRI has not yet been studied in this specific patient subset.

The 6-minute walk test and PFTs will not be used to guide enrollment, but rather will be used in combination with XeMRI/cMRI to assess degree of functional impairment. We will stratify our results based on ethnicity and spirometric abnormalities from those subjects without these findings.

Existing data highlight significant racial and ethnic disparities with historically underserved minority populations (i.e., Black, LatinX) suffering disproportionately higher infection rates and more severe illness compared to Whites. This is reflected by the population enrolled in our RedCAP database and biorepository. As such 30% of subjects enrolled will be required to be from underserved communities.

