2.1 Primary Study Aims

- Aim 1 - Determine the cardiopulmonary structure-function abnormalities that characterize early phase COVID-19 recovery. We anticipate conducting ¹²⁹Xe and cardiac MRI in 13 recovering COVID patients recruited at their clinic visit 60 days' or longer post-discharge from their acute infection. We will recruit patients with new onset persistent and continued dyspnea and to characterize the interstitial, pulmonary vascular and myocardial abnormalities relative to a control population.
- Aim 2 – Characterize the evolution of cardiopulmonary abnormalities over 9 months. Patients will undergo repeat scanning 9 months later to assess changes in all regional parameters acquired from pulmonary and cardiac MRI, directly addressing the possible reversibility of cardiopulmonary limitations arising from “long COVID.”
- Aim 3 – Identify MRI features that predict physiologic outcomes and can alter treatment decisions. Patients will undergo PFTs and quality of life evaluations at 3, 6 and 9 months, as well as detailed clinical histories. These data will be used to understand which baseline imaging features are predictive of long-term quality of life and physiology outcomes as well as those that represent “treatable traits” that can be targeted for therapeutic intervention.

3 Study Design

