4.4.3 Replacement of Early Complete Withdrawal(s)

Subjects who withdraw from the study prior to completing study activities will have the data collected about them used in the primary and secondary endpoint analyses. A new subject will be consented to replace the one withdrawn to ensure data analysis of 23 subjects who have completed all interventions and completed end of study.

5 Standard of Care drugs

Subjects will take their standard of care medication during the necessary time points in the study. There will be no restrictions on concomitant medications.

6 Study Procedures

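### Section 7.1 attaches 90% and 99% power to 23 post-COVID subjects, but Aim 1 compares 13 patients with controls, using non-directional tests and with no stated alpha or control SD

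*Combined protocol and SAP*

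**What the plan says.** Section 7.1 (Sample Size Determination) assumes an absolute difference of 10 percentage points in high barrier uptake between post-COVID subjects and existing healthy controls. The only spread given is a "standard deviation of 10% high barrier uptake within patients". With 90% power, the section says "a two-sided test would require a sample size of 23 to detect a difference". It then argues that high uptake is expected only after COVID, so that "a one-sided test suggests the proposed sample size has 99% power to detect a significant difference". It gives neither a significance level nor an SD for controls.

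Section 2 (Study Objectives) makes the 23 up from two groups: "We will enroll 13 subjects who continue to have respiratory symptoms", and "An additional 10 subjects engaged in competitive sports and diagnosed with COVID-19 will also be enrolled". Of the athletes it says "These subjects can be asymptomatic or mildly to moderately". Aim 1 in Section 2.1 plans "cardiac MRI in 13 recovering COVID patients recruited at their clinic visit" and sets their abnormalities against a control population. Section 4.4.3 replaces withdrawals "to ensure data analysis of 23 subjects who have completed all interventions and completed end of study".

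Section 7.2 (Statistical Methods) compares the groups with about 30 reference subjects by ANOVA or Kruskal-Wallis. It does not say whether athletes are pooled with patients, analysed separately or left out.

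**The concern.** Three things do not fit together.

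- **Population.** The power is computed as if 23 subjects share one 10-point elevation. Aim 1 has 13 such patients. The other 10 may have little or no elevation.
- **Test.** The 99% needs a one-sided test. The analyses named in Section 7.2 are non-directional.
- **Inputs.** Without alpha and a control SD, a reader cannot work out the power of the Aim 1 comparison.

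A reader would credit Aim 1 with 90% to 99% power, and could then take a null result in the 13 patients as stronger evidence of no abnormality than it is. If the athletes are pooled to reach 23, a real difference in the symptomatic patients could be diluted. While the contrast is undefined, that choice could be made after the data are seen.

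**Working it through.** **Inputs.** From Section 7.1: difference 10, patient SD 10. From Section 7.2: about 30 controls. From Section 2: 13 symptomatic subjects and 10 athletes. Assumed, because not stated: alpha 0.05; control SD 10, with 7, 5 and 2 as the range.

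**Method, common SD.** Power comes from the noncentral t distribution with n1 + n2 − 2 degrees of freedom and noncentrality δ = 10 / [10 × √(1/n1 + 1/n2)]. For two groups the two-sided t-test is the same as ANOVA.

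**The plan's own figures**

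- 23 v 23: δ = 1/√(2/23) = 3.39. Power is 91.2% two-sided and 95.5% one-sided. The smallest per-group size reaching 90% two-sided is 23, so the first figure reproduces as a per-group size. Read as 23 in total (11 v 12), it gives only 63%.
- 23 v 30: δ = 1/√(1/23 + 1/30) = 3.61. Power is 94.3% two-sided and 97.2% one-sided.
- 23 v 30, control SD below 10 (Welch, one-sided): 98.6% at SD 8, 99.1% at SD 7, 99.6% at SD 5. So 99% is reached if all 23 carry the full effect and the control SD is about 7 or less.

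**Aim 1 as written: 13 v 30**

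At common SD 10, δ = 1/√(1/13 + 1/30) = 3.01. For a smaller control SD s, the Welch standard error is √(100/13 + s²/30); at s = 5 it is √(7.69 + 0.83) = 2.92, so δ = 3.42.

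| Control SD | Two-sided | One-sided | Difference for 90% two-sided power |
|---|---|---|---|
| 10 (t/ANOVA) | 83.7% | 90.6% | 11.0 points |
| 7 (Welch) | 87% | 93% | 10.5 points |
| 5 (Welch) | 89% | 95% | 10.2 points |
| 2 (Welch) | 91% | 96% | 9.9 points |

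Kruskal-Wallis at common SD 10 gives about 81% (simulation). No row reaches 99%, even one-sided.

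**All 23 pooled v 30, two-sided (simulation)**

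The 13 patients have mean +10 and SD 10. The athletes' mean is an assumption, and their SD is set equal to the control SD. The t-test is used at SD 10 and Welch otherwise.

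| Athlete and control SD | Athletes at 0 | Athletes at +5 |
|---|---|---|
| 10 | 47% | 78% |
| 5 | 74% | 97% |
| 2 | 88% | 99.5% |

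With unaffected athletes the average difference falls to 13 × 10 / 23 = 5.7 points, and mixing the two groups widens the spread.

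**Why Welch for unequal SDs.** With 13 patients at SD 10, 30 controls and no true difference, ordinary ANOVA at nominal 5% rejects about 13% of the time at control SD 5 and 19% at SD 2. Kruskal-Wallis rejects about 9% and 14%. Welch stays at about 5% in both cases.

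**The case against.** No stated number is shown to be miscalculated: 23 per group gives 90%, and 99% one-sided is attainable for 23 v 30. The reference cohort is tightly screened (no smoking or cardiopulmonary history, normal lung function, limits on ventilation defects and RBC/barrier), and Section 7.1 expects high uptake only after COVID. Both suggest a control SD below 10. In that case even 13 v 30 has about 89% to 91% two-sided power, close to the stated 90%. The introduction and Section 4.4.3 speak of 23 subjects, so all 23 v 30 is a possible reading. The athlete effects of 0 and 5 are assumptions. The one-sided 99% is an added remark on which the sample size does not depend. Finally, this is a single-site pilot aimed at feasibility.

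Most of this stands as a limit on the size of the problem. The two-sided shortfall for Aim 1 is moderate and nearly disappears if controls vary little. But the documents give no control SD, so the reader cannot know which case applies. The all-23 reading conflicts with Aim 1's 13 and needs an athlete effect that is nowhere stated. The stratification in Section 2 is by ethnicity and spirometry, not athlete status, so it does not settle the matter. Nothing in the plan supports the one-sided 99% for the tests it names.

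**Conclusion.** The concern holds. The sample size of 23 is defensible as a per-group number; the error lies in the population and the test to which the power is attached. Assuming alpha 0.05, a 10-point difference, patient SD 10 and 30 controls, Aim 1's 13 patients have 84% two-sided power at control SD 10, rising to about 91% at SD 2. The 99% is out of reach for 13 patients over that range, with a one-sided maximum of about 96%. For all 23 it needs a one-sided test, the full effect in athletes and a control SD of about 7 or less. Pooled two-sided power runs from 47% to 99.5% over the athlete effects and SDs tried; that range shows only that the plan does not determine it. This should be fixed, but it does not threaten the study's feasibility aim.

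**What to change.** **Section 7.1.** Delete the one-sided 99% sentence. State alpha and the assumed control SD, taken from the existing reference database. Replacement text along these lines:

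> For Aim 1, the 13 symptomatic subjects are compared with about 30 reference subjects on percent high barrier uptake at two-sided alpha 0.05. Power for a 10-point difference is about 84% if the SD is 10 in both groups (90% for about 11 points), and about 89% to 91% if the reference SD is 5 to 2.

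Once the reference SD is known, keep only the figure that applies. If the sponsor means all 23, say so here and in Aim 1, and state the effect assumed in athletes.

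**Section 7.2.** Name percent high barrier uptake as the powered metric; the current list does not include it. Treat symptomatic, athlete and reference subjects as separate groups, with symptomatic v reference as the Aim 1 contrast. Use an unequal-variance (Welch) test if the reference SD is smaller than the patients'.

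**Cost.** Protocol and SAP wording only. The stated power becomes less favourable; enrolment does not change.

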Statistical Methodology	
¹²⁹Xe MRI metrics will include RBC/barrier, barrier/gas, RBC/gas and several spectroscopic indices. Continuous data will be presented using the mean \pm SD if normally distributed and median with 25th and 75th percentiles otherwise. We are fortunate to be able to compare the findings in our images to a database of approximately 30 healthy reference subjects whom we have scanned to date. These subjects have undergone the same ¹²⁹Xe MRI protocol and were recruited with no histories of smoking or cardiopulmonary disease, FEV1>80%, FEV1/FVC>0.70 and DLCO>80%. For subjects to be included in the reference cohort they further had an RBC/barrier ratio \geq0.45 (at TR=15 ms), and image SNR >5, based on the Rose criterion. Comparisons between these groups will use analysis of variance (ANOVA0 methods or Kruskal-Wallis test as appropriate.

-------------------------	---

CONFIDENTIAL

This document is confidential and the property of the Duke University.

1 Introduction

The next phase of the COVID-19 pandemic is likely to see a surge in associated chronic cardiopulmonary disease that will challenge health systems. Recovered patients are presenting with persistent dyspnea at our Duke Pulmonary Post-COVID clinic. Evidence is now mounting that recovered patients have significant residual pulmonary disease, while myocardial injury has also been increasingly reported. To optimally care for these patients, we must comprehensively assess and monitor the changes in cardiopulmonary function and relate them to physiologic and quality of life outcomes. We will deploy cutting edge MRI to fully characterize cardiopulmonary function in enrolled 23 subjects post recovery and 6-9 months later. Cardiac MRI will assess myocardial status and right ventricular function, while hyperpolarized ^{129}Xe MRI will provide 3D assessment of pulmonary ventilation, interstitial barrier integrity and pulmonary vascular hemodynamics. The overall objective outlined in this study is to demonstrate feasibility and value of comprehensive longitudinal imaging characterization of cardiopulmonary structure and function in patients recovered from Covid-19.

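### Section 7.1's 90% two-sided and 99% one-sided power figures for 23 patients do not fit together, and no one-sided test is planned

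*Combined protocol and SAP*

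**What the plan says.** Section 7.1 (Sample Size Determination) aims to detect an absolute difference of 10% in high barrier uptake between post-COVID subjects and existing healthy controls. It assumes "a standard deviation of 10% high barrier uptake within patients" and 90% power, and concludes that "a two-sided test would require a sample size of 23 to detect a difference". The next sentence changes the sidedness, "given that high-barrier uptake is expected only in the post-COVID group", and states that "a one-sided test suggests the proposed sample size has 99% power to detect a significant difference".

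The proposed size is 23 (Study Summary; section 3.1). Section 4.4.3 replaces withdrawals "to ensure data analysis of 23 subjects who have completed all interventions and completed end of study".

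Section 7.1 gives no alpha, control SD or number of controls, and does not say whether 23 is per group. Section 7.2 describes the comparator as "a database of approximately 30 healthy reference subjects whom we have scanned to date" and the analysis as follows: "Comparisons between these groups will use analysis of variance (ANOVA) methods or Kruskal-Wallis test as appropriate". The Study Summary names the same two tests. Neither place mentions a one-sided comparison.

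**The concern.** The two power figures stand in consecutive sentences, and the only reason given for moving from 90% to 99% is the change from a two-sided to a one-sided test. That change buys a limited and predictable amount of power, and nine points looked like too much.

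The 99% is also the last power figure that a reader meets. It reads as a 1% chance of missing a 10-point difference, and it belongs to a test that the analysis section does not plan. What is at stake is how a non-significant comparison would be read, especially in the 13 patients whom Aim 1 (section 2.1) sets against controls.

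**Working it through.** **Inputs from the plan:** difference 10, patient SD 10, 90% two-sided, 99% one-sided, 23 patients (7.1); about 30 controls (7.2); 13 patients in Aim 1 (2.1). **Assumptions:** alpha 0.05 for either test and control SD 10, both varied below.

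**Step 1: reproduce 23.** The standardised difference is 10/10 = 1. For a two-sample t test the noncentrality is 1/√(1/n1 + 1/n2). With equal groups, noncentral t, two-sided 5%:

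- 22 per group: 89.97%
- 23 per group: 91.25%

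So 23 is the smallest equal group size with 90% power.

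**Step 2: one-sided power from the same inputs.** At 23 v 23 the noncentrality is √11.5 = 3.391.

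- Normal formula: Φ(3.391 − 1.645) = Φ(1.746) = 96.0%
- Noncentral t: 95.5%

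Reaching 99% one-sided with equal groups would take 33 per group (t; 32 by the normal formula).

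**Step 3: does alpha explain it?** Alpha was varied from 0.010 to 0.100 in steps of 0.001, each time taking the smallest equal group size with 90% two-sided power. One-sided power at that size runs only from 94.1% to 96.0%.

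**Step 4: do the unstated control inputs explain it?** By the normal approximation, at a common alpha a,

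one-sided power = Φ(z_two + z(1−a/2) − z(1−a)),

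where z_two is the normal quantile of the two-sided power. The SDs, the number of controls and the allocation do not enter. At a = 0.05:

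- from 90% two-sided: Φ(1.282 + 1.960 − 1.645) = Φ(1.597) = 94.5% one-sided
- from 99% one-sided: Φ(2.326 − 1.960 + 1.645) = Φ(2.011) = 97.8% two-sided
- from 98.5% one-sided, which would round to 99%: 96.8% two-sided

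For alpha 0.01, 0.025, 0.05 and 0.10, 90% two-sided corresponds to 93.7%, 94.1%, 94.5% and 95.0% one-sided.

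**Step 5: scenarios that approach or reach 99%** (alpha 0.05; t test, simulated at control SD 7.3)

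| Comparison | One-sided | Two-sided | Patients enough for 90% two-sided |
|---|---|---|---|
| 23 v 30, control SD 10 | 97.2% | 94.3% | 18 |
| 23 v 30, control SD 7.3 | about 99% | 98% (Kruskal-Wallis 97%) | 12 (Kruskal-Wallis 14) |
| 30 v 30, SD 10 | 98.6% | 96.8% | 23 per group |
| 23 v a fixed value, SD 10 | 99.9% | 99.6% | 13 |

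In the first, second and fourth rows, 23 is no longer what 90% requires. The third uses 30 patients, which is the consent ceiling and not the number enrolled.

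**Step 6: two-sided 5% power of the tests that are planned**, against 30 controls, patient SD 10 (simulation from normal data, ANOVA / Kruskal-Wallis):

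| Control SD | 23 patients | 13 patients |
|---|---|---|
| 10 | 94% / 93% | 84% / 81% |
| 8.3 | 97% / 96% | 90% / 86% |
| 7.3 | 98% / 97% | 93% / 88% |

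The ANOVA figures at unequal SDs are somewhat flattering, because the smaller group has the larger SD.

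**The case against.** The best reply is that section 7.1 never says the two sentences share inputs. The second can be read as a new scenario in which controls show little uptake and so vary less. With 30 controls and a control SD near 7.3, 99% one-sided is about right. This stands in part: the 99% cannot be called wrong in isolation. It does not reconcile the sentences, because that scenario has about 98% two-sided power and needs only 12 to 14 patients for 90%. Nor does the plan state any such inputs.

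The incompatibility also assumes one alpha for both tests. With 30 controls, control SD 7.3, two-sided alpha 0.01 and one-sided alpha 0.05, 23 patients have about 90% two-sided and 99% one-sided power. That is arithmetically correct, but nothing in the plan suggests it, so it only qualifies the conclusion.

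Three further points have some force.

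- The practical effect is modest, since pooled two-sided power exceeds 90% whenever the control SD is 10 or less.
- The 13-patient comparison is not the one that 7.1 powers. It is shown because Aim 1 describes the control comparison for those 13.
- Section 7.2 does not name high barrier uptake among its metrics, and the Kruskal-Wallis figures come from normal data. They are therefore approximate for the setting in which that test would be chosen.

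**Conclusion.** The concern holds. At a common alpha, 90% two-sided and 99% one-sided power cannot both describe the same 23 patients. The inputs that reproduce 23 give 95.5% to 96.0% one-sided, about 3 to 3.5 points below the stated figure. That number rests on alpha 0.05, a common SD of 10 and equal groups; the incompatibility itself does not depend on the SDs, the number of controls or the allocation.

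The 99% also describes no planned test. If the control SD is 10, the planned two-sided tests miss a 10-point difference about 6% to 7% of the time with 23 patients, and about 16% to 19% of the time with 13, not 1%. A smaller control SD narrows this: at 7.3 the miss rates are about 2% to 3% and 7% to 12%. This corrects a stated power figure and does not challenge the sample size.

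**What to change.** In section 7.1:

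1. Delete the one-sided sentence with its 99%.
2. State alpha, whether 23 is per group, the number of controls (about 30), and the control SD read from the existing reference database.
3. State two-sided power for the comparison in section 7.2, 23 patients v about 30 controls. At control SD 10 this is about 94% by ANOVA or 93% by Kruskal-Wallis.
4. Beside it, give the power for the 13 Aim 1 patients v about 30 controls: about 84% or 81% on the same assumption.
5. If the control SD is not 10, replace these figures with ones computed at the observed SD for the test that will be used.

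The cost is a change of wording, one SD from existing data and one power run. The stated power becomes less favourable than 99%; enrolment and design do not change.
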